#### 9.5 Reporting procedures for SAEs

During the trial period, if there is SAE, the researcher should report to the research leader, Peking Union Medical College Hospital and the 81st Hospital of Chinese people's Liberation Army by fax or telephone within 24 hours, and report to CFDA within 24 hours, and report to the ethics committee of the hospital in time.

# 9.6 Emergency unblinding

In case of emergency (such as SAE, or when the subject's medication state must be known before selecting the next treatment strategy), the investigator might break the blindness before the subject's disease progression. If it is necessary to break the blindness, the investigator should inform CRA, the sponsor and the ethics committee. Meanwhile, the time, subject, reason, and process of breaking the blindness should be recorded in the central randomization system

# 10 Data management and statistical analysis

## **10.1 Analysis Set**

- Full Analysis Set (FAS): FAS include all randomized subjects who received at least 1 dose of study treatment. FAS will serve as the main analysis set of efficacy analysis.
- Per-Protocol Set (PPS): PPS will include all subjects in the FAS who did not experience significant protocol deviations which may have impact on the results.
- Safety Set (SS): SS will include all subjects who received at least 1 dose of the study treatment.

## **10.2 Methods of Statistical analysis**

All statistical analysis will be calculated with SAS 9.3 or above. For continuous variables, descriptive statistics including sample size, mean, standard deviation, median, minimum, and maximum, will be presented. For categorical variables, frequencies and percentages will be presented. Survival data will be estimated by Kaplan-Meier method, and K-M plots will be plotted if necessary.

#### **10.2.1 Efficacy analysis**

The median PFS and its 95% Confidence Interval (CI) will be estimated by Kaplan-Meier method, and K-M plots will be plotted; the difference between groups will be tested by unstratified log-rank test. The unstratified Cox proportional hazards regression model will be used for multivariate analysis to compare the difference between groups, and to calculate the hazard ratio (HR) and its 95% CI.

For secondary efficacy endpoints, such as OS and DOR, Kaplan-Meier method will be used to estimate the median and its 95% CI, and the K-M plots will be plotted. The survival between groups will be tested by log-rank test; DCR, ORR and their 95% CI will be calculated, and the differences between groups will be compared by CMH test or Chi-square test.

The primary and secondary efficacy analysis will be performed on FAS; a sensitive analysis

for primary and secondary endpoints will be performed on PPS.

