# 2.2 Secondary Objectives

- To assess the overall survival (OS) in subjects treated with apatinib, compared with placebo.
- To assess the objective response rate (ORR) in subjects treated with apatinib, compared with placebo.
- To assess the disease control rate (DCR) in subjects treated with apatinib, compared with placebo.
- To assess the duration of response (DOR) in subjects treated with apatinib, compared with placebo.
- To assess the time to response (TTR) in subjects treated with apatinib, compared with placebo.
- To assess the safety and tolerability of apatinib, compared with placebo.

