#### **10.3 Sample Size Determination**

The primary endpoint is PFS in subjects with iodine refractory differentiated thyroid cancer treated with apatinib. Referring to the data of phase III clinical trial of sorafenib monotherapy in subjects with DTC (Lancet 2014; 384 (9940): 319-328), assuming a median PFS of 5.8 months in control group, and a median PFS of 12 months in treatment group; subjects randomly assigned to two group by a ratio of 1:1, with an enrollment time of 24 months and a follow-up of 12 months; 50 subjects in each group, to observe 37 PFS events in treatment group and 46 PFS events in control

group, will provide 90% power to detect a difference between groups using a log-rank test with a two-sided significance level ( $\alpha$ )=0.05. Consider a drop-out rate of 15%, 59 subjects in each group are needed, and the total sample size is 118 subjects.

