#### 4.6.2 Duration of overall response

The duration of overall response is measured from the time measurement criteria are first met for CR/PR (whichever is first recorded) until the first date that recurrent or progressive disease is objectively documented (taking as reference for progressive disease the smallest measurements recorded on study).

The duration of overall complete response is measured from the time measurement criteria are first met for CR until the first date that recurrent disease is objectively documented.

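### Section 10.2.1, as worded, most naturally applies a between-arm log-rank test to duration of response, which only responders have, so the p-value would not be a randomised comparison

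*Protocol*

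**What the plan says.** The secondary-endpoint paragraph of Protocol section 10.2.1 names overall survival (OS) and DOR together for estimation: "For secondary efficacy endpoints, such as OS and DOR, Kaplan-Meier method will be used to estimate the median and its 95% CI". After the Kaplan-Meier plots it gives the comparison: "The survival between groups will be tested by log-rank test". Response and disease control rates then get their own tests (CMH or chi-square). DOR gets no other test and is not called descriptive.

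Three other places bear on the reading:

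- Section 2.2 sets the objective "To assess the duration of response (DOR) in subjects treated with apatinib, compared with placebo".
- Section 10.2.1 fixes the analysis set: "The primary and secondary efficacy analysis will be performed on FAS". It has no separate rule for DOR.
- Attachment 1, section 4.6.2, starts the clock at response: "The duration of overall response is measured from the time measurement criteria are first met for CR/PR (whichever is first recorded". The end point is the first documented recurrence or progression.

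**The concern.** A subject who never responds has no start date for DOR. Although the secondary analyses are placed on the FAS, a log-rank test of DOR can therefore use only the responders within it. Whether a subject responds is settled after randomisation and is something apatinib is meant to change; the protocol compares response rates between arms for that reason. Responders on placebo and responders on apatinib are thus selected in different ways, and randomisation no longer makes them comparable. A difference in DOR could reflect who responded rather than what the drug does to an established response. The documents do not allow the direction of that bias to be predicted.

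At stake is the reporting of a secondary endpoint. A significant or non-significant DOR p-value could be cited for or against apatinib when it supports neither. The number of placebo responders may also be too small for the test to exist, or to carry useful information.

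**Working it through.** **1. The stated design, for reference.** The protocol gives no figure for DOR or for placebo response, so there is none to reproduce on that point. The PFS design in section 10.3 does reproduce. Inputs: medians 5.8 and 12 months, 1:1 allocation, two-sided alpha 0.05, 90% power, 24 months of accrual plus 12 of follow-up, 50 per group, 15% drop-out.

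- Hazard ratio = 5.8/12 = 0.483.
- Schoenfeld events = 4(1.960 + 1.282)² / (ln 0.483)² = 80. Freedman events = (1.960 + 1.282)² × (1.483/0.517)² = 87. The stated 37 + 46 = 83 lies between them.
- Power at 83 events: 91.2% (Schoenfeld), 88.7% (Freedman).
- Expected events per 50, with exponential PFS and uniform accrual: 46.1 control, 36.5 treatment.
- 50/0.85 = 58.8, rounded up to 59 per group.

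Nothing here depends on DOR.

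**2. Who can enter a DOR test.** Section 10.2.1 puts secondary analyses on the FAS. Attachment 1, section 4.6.2, starts DOR at first response. Together these leave only FAS subjects with a response. The conditioning problem follows whatever the response rates turn out to be.

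**3. How many placebo responders.** The placebo response rate p is an assumption, shown over 1% to 10%. With n = 59, the expected number is 59p and the chance of none is (1 − p)^59. For example, at 2%, 59 × 0.02 = 1.2 and 0.98^59 = 0.30.

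| Assumed placebo response rate | Expected responders of 59 | Chance of none | Chance of 5 or fewer |
|---|---|---|---|
| 1% | 0.6 | 55% | over 99% |
| 2% | 1.2 | 30% | over 99% |
| 3% | 1.8 | 17% | over 99% |
| 5% | 3.0 | 5% | 93% |
| 10% | 5.9 | 0.2% | 45% |

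With 50 placebo subjects, the number before the drop-out allowance, the expected count is 0.5 to 5.0 and the chance of none 60% to 0.5%.

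**4. What such a test could detect.** Best case: every responder has an event. The apatinib response rate is assumed to be 30% to 90%. The upper end matches the only response figure in the protocol (section 1.3: 9 of 10 partial responses in a single-arm study at 750 mg, a different dose from this trial's starting dose). With r_A and r_P responders, the information is I = r_A × r_P / (r_A + r_P), and power = Φ(|ln HR| × √I − 1.960).

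- Low end, 30% and 2%: I = 17.7 × 1.18 / 18.88 = 1.106. At HR 0.483, power = Φ(0.727 × 1.052 − 1.960) = Φ(−1.195) = 12%.
- High end, 90% and 10%: I = 53.1 × 5.9 / 59.0 = 5.31. Power = Φ(0.727 × 2.304 − 1.960) = Φ(−0.285) = 39%.

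The hazard ratio detectable with 80% power is exp(−(1.960 + 0.842)/√I). This is about 0.07 at a placebo rate of 2%, 0.17 to 0.19 at 5%, and 0.26 to 0.30 at 10%. A higher apatinib response rate hardly helps, because the smaller group governs I.

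**The case against.** The strongest objection is textual. The test sentence speaks of *survival* and does not repeat DOR. Read strictly, it covers OS only, and DOR gets just a Kaplan-Meier median and interval, which is what this review would ask for. That reading is possible. However, the sentence belongs to a paragraph that introduces OS and DOR together, and no other method is offered for the DOR objective, so the broader reading is the more natural one. Under either reading the same clarification removes the doubt.

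It can also be said that the treatment of non-responders is a matter for the statistical analysis plan, which is not at hand. That is fair for the details. The point here is a test that the protocol itself appears to assign, not an omission.

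A reader might infer more than the text supports:

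- **Time to response.** Section 2.2 lists "To assess the time to response (TTR) in subjects treated with apatinib, compared with placebo", but section 10.2.1 does not name this endpoint or give it a test. There is no stated method to correct.
- **A hazard ratio for DOR.** The Cox model and hazard ratio appear only in the PFS paragraph, and none is planned for DOR.
- **Section 2.2 as proof of a test.** The comparison with placebo is attached to every secondary objective, including safety, which section 10.2.2 only summarises by group. A side-by-side description would satisfy it, so section 2.2 need not be reworded.
- **Few placebo responders as a fact.** The protocol gives no placebo response rate, so the counts above are conditional on the assumed range.
- **Unusually slow disease among placebo responders.** Nothing in the protocol shows this, and inclusion criterion 3 requires progression within the 12 months before enrolment.

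**Conclusion.** The concern holds as a point about wording and method for one secondary endpoint. As most naturally read, section 10.2.1 plans a between-arm log-rank test of DOR. That test can include only responders, so its p-value is not a randomised treatment comparison. This conclusion needs no assumed rates; it rests on the reading of section 10.2.1 and on the definition in Attachment 1.

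The size of the practical problem does rest on assumptions. If the placebo response rate is 1% to 10%, about 0.6 to 5.9 placebo responders are expected among 59, with a 55% to 0.2% chance that the test cannot be computed at all. Where it can be computed, power is 12% to 39% at the PFS hazard ratio, for placebo rates of 2% to 10%, apatinib rates of 30% to 90%, and an event in every responder.

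Severity is low. The sample size and the interim efficacy rule rest on PFS, and no decision rule depends on DOR.

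**What to change.** In section 10.2.1, limit the log-rank sentence to OS. Add that DOR is reported descriptively by arm among responders: number of responders, Kaplan-Meier median and 95% CI, with no between-arm p-value. State that this set is the responders within the FAS, so that the analysis-set sentence is true for DOR as well.

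The cost is one or two sentences, with no new data and no change to PFS, alpha or sample size.

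An analysis of time in response over a fixed window in all FAS subjects, counting non-responders as zero, would restore a comparison of the arms on the whole FAS. It is optional: it is a new endpoint and would need a chosen window and rules for death, censoring and the switch of placebo subjects to apatinib.

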#### 10.2.2 Safety analysis

Safety analysis will be performed on the Safety Set.

AEs will be coded as low-level terms, preferred terms and major system organ classes (SOC) using MedDRA (v20.0 or higher version).

Treatment emergent adverse events (TEAEs) is defined as any AE that is new or aggravated from baseline (before study treatment) after the initiation of medication.

Only TEAEs will be summarized. All AEs, TEAEs or other indications will be listed.

The incidence of TEAEs will be summarized according to the number and percentage of major system organs and preferred terms. Under the same system organ classification and standard terminology, if the event occurs for multiple times, the subjects only calculate the highest level of the event. The number and incidence of TEAEs are also summarized according to their relationship to treatment.

The frequencies and percentages of AEs, SAEs,  $\geq$ Grade 3 AEs,  $\geq$ Grade 3 SAEs, drug-related AEs, drug-related SAE, AEs with incidence rate  $\geq$ 5%, SAEs with incidence rate  $\geq$ 5%, AEs leading to dose adjustment, AEs leading to termination of treatment will be summarized by group. If necessary, for AEs with special interest, Kaplan-Meier method will be used to analyze the occurrence time and duration of events.

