# 3 Study Design and Methodology

# 3.1 Overall Study design

This is a multicenter, randomized, double-blind, placebo-controlled clinical trial to evaluate the efficacy and safety of apatinib in the treatment of locally advanced/metastatic radioiodine refractory differentiated thyroid cancer (RAIR-DTC).

The eligible subjects will be randomly assigned to either the treatment group or control group in a 1:1 ratio. Apatinib or placebo will be given 500 mg orally once daily for 28 days. Apatinib treatment will be discontinued at the time of disease progression, intolerable toxicity, withdrawal of consent, or due to investigator's evaluation. Tumor imaging with CT or magnetic resonance imaging (MRI) will be done at the end of first and second treatment cycles, then every two treatment cycles thereafter. The efficacy will be assessed per RECIST version 1.1 by investigators. Safety assessment including vital signs, physical examination, blood and urine analysis, liver, kidney and thyroid function tests, electrolyte profile, electrocardiogram and ECOG performance status will be done every two weeks for one-two cycles, and at the end of each subsequent cycle. Adverse events will be graded according to the National Cancer Institute Common Terminology Criteria for Adverse Events (version 4.0). Survival status will be followed up every two months until death or loss to follow-up.

In the extension phase, subjects in the Apatinib group will continue the treatment when anticipated to benefit from apatinib treatment. For the subjects in the control group, they will be allowed to receive apatinib upon experiencing radiographic disease progression (PD) per RECSIT v1.1 by investigator. Extended treatments are terminated after progression disease, intolerable toxicity, and withdrawal of informed consents during extension phase.

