## 3.3 Sample Size

Sample size determination is performed by PASS 11 software with group sequential log-rank test settings. Assuming a median PFS of 5.8 months in control group, and a median PFS of 12 months in treatment group; subjects randomly assigned to two group by a ratio of 1:1, with an enrollment time of 24 months and a follow-up of 12 months; 50 subjects in each group, to observe 37 PFS events in the treatment group and 46 PFS events in the control group, will provide 90% power to detect a difference between groups using a log-rank test with a two-sided significance level ( $\alpha$ )=0.05. With a 15% drop-out rate, each group will require 59 people, for a total sample size of 118 subjects.

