#### 3) At the end of the third week after the start of administration and after

Vital signs, physical examination (including skin toxicity, nausea, fatigue, tooth function such as looseness, tooth drop, etc.), ECOG PS score, life quality score, blood routine, urine routine, stool routine, liver and kidney function test, electrolyte test, blood coagulation function test and electrocardiogram examination are performed weekly, in case of precordial pain, palpitation and other symptoms, the myocardial enzyme spectrum should be detected immediately, and cardiac color Doppler ultrasound should be performed (subjects can increase the frequency of selfexamination of vital signs according to their own situation and fill in the relevant abnormal conditions in the research diary. The above examination is changed to once every 2 cycles after 6 cycles of medication.

The efficacy of tumor is evaluated every 2 cycles (imaging examination: CT/MRI/B ultrasound), serum Tg and TgAb levels are detected, and thyroid function is examined.

Blood pressure monitoring: the subjects should self-monitor the blood pressure at least once a week, once abnormal, they need to monitor to the normal level every day, and record in the patient's diary card. During the visit, the researcher measures the blood pressure, and the measurement method is the same as that in the first cycle.

4) The concomitant medication and AE should be observed and recorded at any time from the beginning of administration to 30 days after the end of administration.

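### By-group adverse event percentages take no account of the roughly 1.6-fold longer observation that the plan's own PFS medians imply for the apatinib arm

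*Protocol*

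**What the plan says.** Section 2.2 makes safety and tolerability compared with placebo a secondary objective. Section 10.2.2 sets out the tables that serve it: TEAEs by system organ class and preferred term as number and percentage, then frequencies and percentages of AEs, SAEs, Grade 3 or higher events, drug-related events and events with incidence of at least 5%, and finally "AEs leading to dose adjustment, AEs leading to termination of treatment will be summarized by group". For drug-related events, section 9.4 sets the denominator as all subjects evaluated for safety. The only time-based method is Kaplan-Meier, if necessary, for events of special interest.

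Under sections 3.1 and 5.1.2, study drug stops at progression, intolerable toxicity, withdrawal of consent or the investigator's decision. Section 10.3 plans the trial "assuming a median PFS of 5.8 months in control group, and a median PFS of 12 months in treatment group", "with an enrollment time of 24 months and a follow-up of 12 months".

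The observation window is described in several ways. Section 7.3, item 4, has adverse events "observed and recorded at any time from the beginning of administration to 30 days after the end of administration", and section 7.6 also follows subjects for 30 days after the last dose. Section 9.1 monitors from enrolment to the end of the study. The TEAE definition in section 10.2.2 has a start but no end. Sections 3.1, 7.4 and 8 let control subjects take open-label apatinib after progression, and section 7.4 lets apatinib subjects continue open-label.

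**The concern.** A percentage of subjects with at least one event rises with the time each subject is watched. If the drug works as planned, apatinib subjects stay on treatment, and under observation, much longer than control subjects. An event unrelated to the drug that arises at a steady rate will then be reported in more apatinib subjects. The prescribed tables would not show how much of a difference reflects the drug and how much reflects longer observation. The listing of events with incidence of at least 5% is exposed in the same way, because longer observation alone can carry an event over the threshold in one arm.

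The missing end date for TEAEs adds a second difficulty. If events on open-label apatinib count under the randomised group, drug toxicity enters the control percentage and the bias can run the other way.

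**Working it through.** **Inputs.** Section 10.3: medians 5.8 and 12 months, 24 months of accrual, 12 months of follow-up, 50 evaluable and 59 randomised per arm. Sections 7.3 and 7.6: 30 days after the last dose. Assumptions not in the protocol: exponential PFS, uniform accrual, treatment exactly to progression, and the event hazards below.

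**The plan's own figure first.** Hazards of progression are λ = ln 2/5.8 = 0.1195 and ln 2/12 = 0.0578 per month. The probability of an event by the end of the study is

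P(r) = 1 − (e^(−12r) − e^(−36r))/(24r).

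This gives 0.922 on control and 0.729 on apatinib, so 50 per arm yield 46.1 and 36.5 events. Section 10.3 states 46 and 37, so the model matches the plan's design.

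**Time on drug.** Mean time on drug is P(λ)/λ: 0.9216/0.1195 = 7.7 months and 0.7295/0.0578 = 12.6 months, ratio 1.64. Adding 30 days (0.99 month) to each gives 8.7 and 13.6 months, ratio about 1.6.

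**Crude incidence with no drug effect.** Give both arms the same constant event hazard μ. The proportion with a first event on drug is p = μ × P(λ+μ)/(λ+μ). With the 30-day window it is 1 − (1 − p)e^(−0.99μ).

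| μ per 100 patient-months | On drug: control v apatinib | With 30 days: control v apatinib |
|---|---|---|
| 1 | 7.2% v 11.5% | 8.1% v 12.4% |
| 3 | 19.2% v 29.2% | 21.5% v 31.3% |
| 6 | 32.5% v 46.8% | 36.4% v 49.9% |

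The excess is about 4 to 14 percentage points. At 3 per 100 with 59 per arm, that is about 11 v 17 subjects (59 × 0.192 and 59 × 0.292). At 0.5 per 100 the on-drug figures are 3.7% and 6.0%, on either side of the 5% threshold.

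**The same data per unit of time.** Subjects with a first event divided by time at risk to first event is p ÷ [P(λ+μ)/(λ+μ)] = μ in each arm, so the ratio is 1.00.

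**Where the distortion is small.** If events arise only in the first two cycles (56 days, 1.84 months), p = μ/(μ+λ) × (1 − e^(−1.84(μ+λ))). At 5 per 100 this gives 7.9% v 8.3%, and at 10 per 100 it gives 15.1% v 16.0%, ratios of 1.05 to 1.06.

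**If toxicity shortens apatinib treatment.** Add an assumed stopping hazard to λ in the apatinib arm only. At 2 per 100 patient-months, mean time on drug falls to 10.6 months (ratio 1.37). At 5 per 100 it falls to 8.4 months (ratio 1.09).

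**The case against.** The strongest reply is that crude TEAE tables by arm are conventional, that section 10.2.2 specifies no between-arm test, and that exposure-adjusted rates are often left to a statistical analysis plan, which is not at hand. This limits the severity. It does not remove the point, because section 10.2.2 lists its safety outputs in detail, section 2.2 sets the comparison with placebo, and the listed outputs are not like-for-like under the protocol's own medians.

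It is also fair that the size rests on constant hazards and on treatment lasting to progression. Both limits are shown in the working.

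A reader might go further and infer from "The above examination is changed to once every 2 cycles after 6 cycles of medication" that sparser testing in later cycles helps to make the arms differ. The documents do not support that. One rule applies to both arms by time on treatment, and adverse events are recorded at any time. Sparser testing would also remove late detections mainly from the longer-treated arm: if detection halved after cycle 6, the crude ratio at 1 per 100 would fall from 1.60 to 1.46. Kaplan-Meier curves compare the arms at equal time since start, hence under the same schedule, so there is no reason to truncate them at cycle 6. Restricting laboratory events to cycles 1 to 6 would not provide one uniform schedule across tests (section 7.1), and it leaves a gap of 3.9% v 4.6% at 1 per 100 and 21.0% v 24.4% at 6 per 100.

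Nor may a reader conclude that any observed difference arises by construction rather than from the drug. Real effects also enter the percentages, and early-onset events are barely affected.

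**Conclusion.** The point holds as a moderate weakness of the safety analysis. Under the planning assumptions, apatinib subjects are observed about 1.6 times as long, and a steady-rate event with no drug effect shows an excess of about 4 to 14 percentage points at hazards of 1 to 6 per 100 patient-months. The figures assume exponential PFS, treatment to progression and a constant event hazard. They fall to a ratio of 1.05 to 1.06 for events confined to the first two cycles, and they fall if toxicity stops shorten apatinib treatment.

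The direction is not guaranteed either. It depends on which adverse event window is applied and on whether events on open-label apatinib count against the control arm, and the protocol leaves both unsettled.

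**What to change.** Keep the crude tables in section 10.2.2. For the same categories and by arm, add exposure-adjusted first-event incidence: subjects with a first event per 100 patient-months at risk on randomised treatment plus 30 days. In the control arm, count only events before any open-label apatinib. Report extension-phase events in separate tables. Reconcile the adverse event windows in sections 7.3 (item 4), 7.6, 9.1 and 10.2.2, so that the TEAE definition has a stated end.

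The cost is a few extra tables from data the protocol already collects and a paragraph of protocol or analysis-plan wording. Exposure-adjusted rates assume a roughly constant hazard and can mislead for front-loaded events, so they should be read beside the crude tables and not in their place.
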